14.1.3 Concomitant Therapies

Ataluren has not proved allergenic in studies performed to date, but review of known allergies to excipients contained in the formulation is prudent. The restriction on concurrent involvement in other therapeutic clinical trials is intended to avoid confounding effects.

14.1.4 Safety Profiling

As is conventional, safety will be characterized in terms of the type, incidence, timing, severity, drug-relatedness, and seriousness of adverse events and laboratory abnormalities. For consistency of interpretation, adverse events will be coded using the MedDRA, the severity of these events and laboratory abnormalities will be graded using the well-defined CTCAE, Version 3.0, and concomitant medications will be coded with the WHODRUG dictionary.

14.1.5 Study Drug Compliance

Evaluation of study drug compliance provides context for assessments of pharmacological activity, safety, and PK, and may offer a general indication of patient acceptance of therapy, integrating factors of tolerability, palatability, and convenience. The compliance of the patient will be verified by counting unused drug study sachets.

14.1.6 Trough Ataluren Plasma Concentrations

Collection of plasma for ataluren concentrations is important for confirming maintenance of exposure over time. Having these data may allow correlations of exposure with measures of efficacy and toxicity. Because the ataluren PK profile has been well characterized in existing Phase 2a and Phase 3 studies in patients with CF, plasma sampling will be limited to before

dosing relative to the morning dose at each clinic visit. This will provide information regarding ataluren trough concentrations. The high performance liquid chromatography with tandem mass spectrometry (HPLC/MS-MS) method that will be used to quantify ataluren plasma concentrations has been fully validated in the context of the prior Phase 1 and Phase 2 studies. Plasma samples will be retained for potential later analyses of ataluren metabolites or corticosteroid parent drug and metabolites.

14.1.7 Timing of Assessments

The timing of study assessments is appropriate in the context of a chronic study, permitting inclusion of 8 post-baseline evaluations during the study period, ensuring that time trends can be adequately assessed and that sporadically missing data do not have a substantial impact on data analysis. The visit frequency also give consideration the need for many patients to travel considerable distances to study sites and that sites may achieve limiting capacity to accomplish study visits and data flow once multiple patients are being followed simultaneously at a single site.

Study activities have been mapped across the study as outlined in the Schedule of Events (see Table 3).

14.2. Treatment and Safety Monitoring Plan

14.2.1. Schedule and Dose Selection

Dosing based on body weight will continue to be employed. Such dosing reduces variability in exposure by accommodating differences in patient size across the span of ages in patients who will participate in the clinical study program.

The schedule of drug administration is derived directly from Phase 1 PK modeling and from Phase 2 exposure information. The intent of administering two smaller doses at 6-hour intervals during the day and a larger dose at a 12-hour interval overnight (eg, at 7:00 AM, 1:00 PM, and 7:00 PM) is to optimally sustain target plasma concentrations while minimizing total exposures. This schedule is likely to fit well with daily patterns of living for patients, thus enhancing compliance.

14.2.2. Duration of Therapy

This open-label study is expected to generate at least 96 weeks of safety information. This information will supplement safety data obtained from the randomized, placebo-controlled, double-blind study (PTC124-GD-021-CF), which has a planned treatment duration of 48 weeks.

14.2.3. Safety Monitoring Overview

In response to the occurrence of renal toxicology findings in the mouse and renal laboratory abnormalities in prior ataluren studies, the renal safety monitoring plan utilized for the previous Phase 3 study is also appropriate for renal monitoring of this study population. Thresholds for evaluation and intervention have been established for other types of adverse events or laboratory abnormalities observed in the study, including hepatic abnormalities. The intent is to protect patients, obtain a thorough assessment of any clinically relevant adverse events or laboratory abnormalities, and to offer recommendations for interruption and dose modification of study drug in response to potential safety signals. The nature of these risks and the measures to monitor for them will be reflected in the informed consent form.

As noted in Section 6.3.1, patients must be monitored closely for adverse events or laboratory abnormalities during the course of the study. Section 6.3.1 provides information on actions to be taken in the event that abnormalities are noted on specified monitoring studies. Thresholds are provided for interrupting study drug immediately, for interrupting study drug after confirmation of a value beyond the threshold, or for continuing study drug while evaluating for potential drug-related toxicity.

14.2.4. Renal Monitoring Plan

Renal findings were seen in mice receiving one or two doses through 26 weeks of dosing with ataluren. A no-observed-adverse-effect level (NOAEL) for the renal toxicity findings in mice has not been identified; the lowest observed adverse effect level (LOAEL) = 75 mg/kg/day. Exposure in mice at 75 mg/kg/day is 0.3-fold the exposure in patients administered ataluren at the morning, midday, and evening doses of 10, 10 and 20 mg/kg/day, respectively. The renal finding was seen primarily in the distal nephron and involved some degenerative changes (apoptosis) and regenerative changes (proliferation of renal epithelium) accompanied by tubular dilatation and proteinaceous material within the tubules. Rarely the tubules were mineralized. Fibrosis was not seen after 1 month of dosing, but an interstitial renal fibrosis was observed in the 26-week carcinogenicity study in mice. The finding was occasionally accompanied by individual increases in serum blood urea nitrogen (BUN) and/or creatinine, but a dose relationship for these parameters was not observed. The kidney findings were partially to completely reversible as soon as 2 to 6 weeks after cessation of dosing. The renal toxicity was observed in mice only, and has not been seen in rats dosed for 24 months or in dogs dosed for 52 weeks despite achievement of exposures in rats and dogs that were comparable to or greater than those observed in mice.

In the Phase 3 clinical trial (Study 009), serious adverse events related to renal dysfunction, which occurred only in the ataluren arm, included 3 patients with acute renal failure, 3 patients with renal failure, and 1 patient with hypercreatininemia. These events were characterized by elevated creatinine (Grade 1 to Grade 4), which resolved over days to weeks. Only 1 patient experienced symptoms of renal dysfunction (transient oliguria). All 7 events were associated with concomitant systemic treatment with potentially nephrotoxic antibiotics (eg, aminoglycosides, vancomycin) that were generally administered as treatment for pulmonary exacerbations. No patient required dialysis. One patient was unblinded and 1 patient chose not to continue study drug treatment; the remaining 5 of 7 patients restarted study medication and continued study participation without recurrent creatinine elevations. This issue was recognized during the conduct of the study and changes were made in the protocol (eg, prohibition of concomitant use of potentially nephrotoxic agents), which successfully addressed the issue.

Non-serious creatinine elevations occurred predominantly in the ataluren arm and were transient, generally mild, and resolved with or without interruption of study medication. The incidence of treatment emergent nephrolithiasis was similar in the ataluren and placebo groups.

Non-serious episodes of creatinine elevation in Study 009 occurred predominantly in the ataluren arm and were transient, generally mild, and resolved with or without interruption of study medication. However, there was no clinically meaningful difference in creatinine between the ataluren and placebo arms at Week 48, indicating that there was no cumulative effect of these transient elevations on renal function. The incidence of treatment-emergent nephrolithiasis was similar in the ataluren and placebo groups.

The renal monitoring program included in this protocol considers nonclinical and clinical findings with ataluren and past experience with known nephrotoxicants. Concomitant use of potentially nephrotoxic antibiotics with ataluren is prohibited. A focus is placed on well-established clinical indictors of renal dysfunction for making diagnostic decisions and prompting treatment interruptions/ modifications in individual patients. The rationale for each of the decision-making parameters is discussed below.

- Serum Creatinine: Given the widespread clinical familiarity with serum creatinine as a marker of renal dysfunction and as a monitoring tool for nephrotoxins in clinical practice [Gilead 2002, Gilead 2006, Novartis 2005], characterization of serum creatinine provides an appropriate frame of reference relative to other experiences.
- Serum Cystatin C: An alternative to assessing GFR based on serum creatinine, serum cystatin C offers advantages in the assessment of renal function in the context of this protocol. Cystatin C is a low-molecular-weight {~13 kDa} proteinase inhibitor derived from all cells that is filtered by the glomerulus and degraded in the renal tubules [Herget-Rosenthal 2007]. The serum cystatin C concentration is almost solely dependent upon GFR and appears relatively unaffected by muscle mass or other conditions. An additional advantage is that circulating cystatin C changes more rapidly in response to multiple types of renal injury than creatinine [Herget-Rosenthal 2007]. Methods for measuring cystatin C are standardized and the correlations between serum cystatin C and GFR have been derived and confirmed in large studies involving healthy children and adults and those with renal dysfunction [Dharnidharka 2002, Grubb 2005, Zappitelli 2007]. Based on these considerations, values of serum cystatin above 1.33 mg/L should prompt diagnostic evaluation and interruption/modification of study drug if required per protocol.
- Serum Blood Urea Nitrogen: Considering its role in maintaining urine-concentrating ability, urea has major importance in renal physiology and its clinical measurement as a marker of renal dysfunction is long established. In the context of nephrotoxicity, elevations in BUN suggest disruption of tubular integrity [Vonderscher 2007]. In the nonclinical mouse studies of ataluren in which nephrosis were observed, BUN was elevated in some of the affected animals, confirming that this marker should also be measured in clinical studies of ataluren. Monitoring serum BUN, like monitoring creatinine, provides an additional frame of reference relative to other markers assessed within this study and in other studies of known nephrotoxicants. However, an elevation in BUN is not a specific signal of renal tubular injury, but also may reflect compromised renal tubular blood flow due to depressed cardiac output, medications, or dehydration [Guignard 2004, Stevens 2007]. For these reasons, a BUN increase ≥1.5 x ULN should prompt a review of potential pre-renal, renal, and post-renal causes for the abnormality as well as consideration of potential interruption/modification of study drug dosing.
- **Renal Ultrasound**: In considering the markers to be used for decision-making within the study, renal ultrasound is proposed because it is the central imaging modality for assessing the anatomy of the kidneys and urinary tract in children. The test can detect changes in kidney size, assess parenchymal cystic or mass lesions, evaluate the renal vasculature, and assess the collecting system [Avni 2004]. Renal ultrasound is a routine component of diagnostic algorithms for follow-up of serum or urinary abnormalities suggesting renal dysfunction [Barratt 2004] and will be among the diagnostic testing performed for this

protocol as part of the assessment for such findings. It is safe, painless and convenient, providing advantages over contrast-enhanced computed tomography (CT) scanning (which has contrast-mediated nephrotoxicity and radiation risks) and magnetic resonance imaging (MRI) (which requires contrast administration and potential sedation in young children). Obtaining a baseline ultrasound enhances the sensitivity of subsequent ultrasonography, offering context for any potential abnormalities emerging during study drug treatment. An end-of-study ultrasound offers further reassurance that the kidneys remain anatomically normal at the completion of this protocol.

14.2.5. Hepatic Monitoring Plan

CF-related hepatobiliary obstruction and inflammation may result in serum transaminase elevations. Consequently, it is not practical to exclude patients with modestly increased serum AST, ALT, or GGT concentrations from enrollment in the Phase 3 study, and monitoring for hepatotoxicity in patients with preexisting disease must rely on observing changes from baseline in these parameters while also looking for increases in bilirubin. Consistent with well-established guidelines [Abboud 2007] applied in this disease setting, even modest (Grade 2) alterations in bilirubin should prompt interruption of study drug, once abnormal value is confirmed (per Table 2).

In the Phase 2a experience with ataluren in nmCF, reductions in serum markers of hepatic injury (particularly ALT) were observed [Clancy 2006], although no significant changes were seen in a larger-scale Phase 3 study. Since no significant changes in hepatic serum markers were observed in the Phase 3 study, these markers are not included in this protocol as efficacy assessments. Therefore, the hepatic monitoring in this study is being performed as part of the general safety monitoring.

14.2.6. Blood Pressure Assessment

During the Phase 2b double-blind study of ataluren in nmDMD (PTC124-GD-007-DMD), 6 patients – all receiving corticosteroids – had hypertension (or increased blood pressure) reported as adverse events (0 for ataluren 20-, 20-, 40-mg/kg, 5 for ataluren 10-, 10-, 20-mg/kg, and 1 for placebo. During the double-blind Phase 3 study of nmCF (Study 009), changes in systolic and diastolic blood pressure were small and not clinically meaningful. No substantial shifts in systolic or diastolic blood pressure from below to above the 95th and/or 99th percentile (adjusted for age and height) from baseline to Week 48 were observed in the ataluren group. In this study, blood pressure will be monitored via standardized procedure at each visit.

14.2.7. Other Nonclinical Findings

Single lipomatous, non metastatic tumors, determined to be malignant hibernomas originating in brown adipose tissue were identified in 6 rats during a 26 week toxicity study. In a second 26-week rat study, no malignant hibernomas were observed in any dose group, including the high dose group (1200 mg/kg/day). The exact correlative relevance of this finding is unclear given the lack of reproducibility in rats, the different physiology of brown fat in rats relative to humans [Cannon 2004, Iatropoulos 2004], the very young age of the rats used in these studies, the lack of ataluren genotoxicity, and the extreme rarity and generally benign course of hibernomas in humans [Furlong 2001].

Urinary bladder tumors were observed in 3/60 females at the high dose of 300 mg/kg/day in the 24-month carcinogenicity study in rats. This dose exceeded the maximum tolerated dose

(MTD), based on an average 23% reduction in body weight gain in comparison to vehicle controls throughout the study. In addition, the proposed mode of urinary bladder tumor formation (presence of calculi) in rats is not considered relevant to humans. Mean steady state exposures in female rats at the mid-dose of 100 mg/kg/day and in male rats at the high-dose of 300 mg/kg/day were 4 and 6 times, respectively, the steady state exposure in patients administered ataluren at the morning, midday and evening doses of 10-, 10-, and 20-mg/kg/day, respectively.

Long-term post-treatment follow-up safety data currently available, some for over 7 years, from the patients dosed with ataluren to date in the clinical studies, indicate no increased risk of tumors. Long-term outcomes will be collected by completion of long-term health surveys after completion of ataluren or through a post-approval registry.

14.2.8. Other Abnormalities

Recommendations for interruption of dosing are provided in Section 6.3.1, with the general intent that a Grade 4 (life-threatening) event should result in immediate cessation of study drug while awaiting confirmation of the abnormal laboratory value, a Grade 3 (severe) event may require confirmation of the abnormal laboratory value before cessation of dosing, and a Grade 2 (moderate) event may prompt further evaluation while study drug dosing continues. It is intended that these recommendations be viewed flexibly; the type and context for any adverse event or laboratory abnormality must be considered in taking action.

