6.3. Safety Monitoring and Study Drug Dose Interruption/Modification

6.3.1. Laboratory Abnormalities and Adverse Events Requiring Evaluation and Potential Drug Interruption/Modification

Patients must be monitored closely for adverse events or laboratory abnormalities during the course of the study.

For adverse events or laboratory abnormalities, the investigator will use judgment in determining whether the event or abnormality is clinically significant, whether diagnostic evaluation is warranted, and whether potential interruption of study drug treatment is appropriate. In general, life-threatening (Grade 4) or severe (Grade 3) adverse events or laboratory abnormalities should be considered clinically significant, although recurrent or persistent moderate events (Grade 2) may also be considered clinically significant in certain circumstances. Reference should be made to the Common Terminology Criteria for Adverse Events (CTCAE), Version 3.0 (see *http://ctep.cancer.gov/protocolDevelopment/electronic_applications/docs/ctcaev3.pdf* for grading the severity of adverse events and laboratory abnormalities.

Table 2 provides information on actions to be taken in the event that abnormalities are noted in specified laboratory parameters. Thresholds are provided for interrupting study drug immediately, for interrupting study drug after confirmation of a value beyond the threshold, or for continuing study drug while evaluating for potential drug-related toxicity. For adverse events or laboratory abnormalities not listed in Table 2, the investigator should use his/her judgment in determining whether the event or abnormality is clinically significant, whether diagnostic evaluation is warranted, and whether potential interruption of study drug is appropriate.

Organ System and Laboratory Parameter	Stop Study Drug Immediately, Confirm Abnormal Value, and Then Start Work-Up ^a	Stop Study Drug After Confirming Abnormal Value, and Then Start Work-Up ^a	Continue Study Drug, Confirm Abnormal Value, and then Start Work-Up ^a
Hepatic			
Serum total bilirubin ^b	≥Grade 3 (≥3.0 x ULN)	Grade 2 (1.5 – 3.0 x ULN)	
Serum ALT	≥Grade 3 (≥5.0 x ULN)	Grade 2 (>2.5 – 5.0 x ULN)	
Serum AST	≥Grade 3 (≥5.0 x ULN)	Grade 2 (>2.5 – 5.0 x ULN)	
Serum GGT	≥Grade 3 (≥5.0 x ULN)	Grade 2 (>2.5 – 5.0 x ULN)	
Renal			
Serum cystatin C	>2.00 mg/L	>1.33 – 2.00 mg/L	
Serum creatinine	≥ Grade 2 (≥1.5 x ULN for	Grade 1 (>ULN – 1.5 x ULN for	
Serum creatinine	age)	age)	

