As necessary, laboratory abnormalities will be described by duration of study drug exposure, by dose, by age group, by sex, by race, by weight, and for special populations (eg, antibiotic use).

Table 2. Safety Monitoring Parameters and Actions To Be Taken

| Organ System and Laboratory Parameter | Stop Study Drug Immediately, Confirm Abnormal Value, and Then Start Work-Up ^a | Stop Study Drug After Confirming Abnormal Value, and Then Start Work-Up ^a | Continue Study Drug, Confirm Abnormal Value, and then Start Work-Up ^a | |
|--|---|--|--|--|
| Hepatic | | | | |
| Serum total bilirubin ^b | ≥Grade 3 (≥3.0 x ULN) | Grade 2 (1.5 – 3.0 x ULN) | | |
| Serum ALT | ≥Grade 3 (≥5.0 x ULN) | Grade 2 (>2.5 – 5.0 x ULN) | | |
| Serum AST | ≥Grade 3 (≥5.0 x ULN) | Grade 2 (>2.5 – 5.0 x ULN) | | |
| Serum GGT | ≥Grade 3 (≥5.0 x ULN) | Grade 2 (>2.5 – 5.0 x ULN) | | |
| Renal | | | | |
| Serum cystatin C | >2.00 mg/L | >1.33 – 2.00 mg/L | | |
| Serum creatinine | ≥ Grade 2 (≥1.5 x ULN for age) | Grade 1 (>ULN – 1.5 x ULN for age) | | |
| Serum BUN | ≥3.0 x ULN | ≥1.5 – 3.0 x ULN | | |

^a Laboratory abnormalities may be confirmed immediately or at the next scheduled clinic visit based on investigator judgment.

Abbreviations: ALT = alanine aminotransferase, AST = aspartate aminotransferase, BUN = blood urea nitrogen, GGT = gamma glutamyl transferase, ULN = upper limit of normal

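### Protocol 14.2.8 summarises the stop-drug rules more leniently than Table 2 (by one grade for four hepatic tests, two for creatinine), and Table 2's continue column is empty

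*Protocol*

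**What the plan says.** Protocol 14.2.8 (Other Abnormalities) opens by naming its source: "Recommendations for interruption of dosing are provided in Section 6.3.1, with the general intent that" certain grades lead to certain actions. It then gives three tiers:

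- Top tier: "a Grade 4 (life-threatening) event should result in immediate cessation of study drug while awaiting confirmation of the abnormal laboratory value"
- Middle tier: for Grade 3, the laboratory result may have to be confirmed first and drug stopped only afterwards.
- Lowest tier: "a Grade 2 (moderate) event may prompt further evaluation while study drug dosing continues"

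The next sentence asks that the recommendations be read flexibly and in context.

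Table 2, in Protocol 6.3.1, has three action columns: stop at once, stop after confirmation, and continue while confirming. SAP 4.10.2 reproduces the table, including the middle column headed "Stop Study Drug After Confirming Abnormal Value, and Then Start Work-Up". Entries appear in the first two columns only.

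The text of 6.3.1 introduces the table as giving thresholds for both kinds of interruption, "or for continuing study drug while evaluating for potential drug-related toxicity". Section 14.2.3 repeats that statement. For abnormalities not in Table 2, 6.3.1 leaves interruption to the investigator's judgement.

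Section 14.2.5, on hepatic monitoring, says that "even modest (Grade 2) alterations in bilirubin should prompt interruption of study drug" once the value is confirmed, and cites Table 2.

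**The concern.** Three parts of one protocol describe the same interruption recommendations, and they do not agree. A reader who takes 14.2.8 as a summary of 6.3.1 gets a later trigger than a reader who goes to Table 2. The tier that 14.2.8 fills with Grade 2 events is the tier that Table 2 leaves blank.

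This matters because the primary objective (Protocol 3.1) is long-term safety, judged by adverse events and laboratory abnormalities. Renal and hepatic tests are the ones given explicit stop thresholds. Section 14.2.4 reports seven renal serious adverse events in Study 009, all in the ataluren arm and all with concomitant systemic, potentially nephrotoxic antibiotics. Section 14.2.9 says that the recommendations are meant to encourage a consistent approach, and two versions of the thresholds work against that aim.

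**Working it through.** No sample size, power or event figure is involved. The check sets the trigger grade for each action in 14.2.8 beside the trigger for the same action in Table 2, then counts the entries in the continue column.

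**Step 1. Trigger grades side by side**

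| Action | 14.2.8 | Table 2: bilirubin, ALT, AST, GGT | Table 2: creatinine |
|---|---|---|---|
| Stop at once | Grade 4 | Grade 3 or higher | Grade 2 or higher |
| Stop after confirmation | Grade 3 | Grade 2 | Grade 1 |
| Continue and evaluate | Grade 2 | blank | blank |

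**Step 2. Offset (14.2.8 grade minus lowest Table 2 grade)**

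- Four hepatic parameters: stop at once, 4 − 3 = 1; stop after confirmation, 3 − 2 = 1.
- Creatinine: stop at once, 4 − 2 = 2; stop after confirmation, 3 − 1 = 2.
- Cystatin C and BUN: Table 2 gives numeric limits (for example above 2.00 mg/L, or 3.0 x ULN and over) with no CTCAE grade, so no offset can be formed.

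Five of the seven parameters can be compared, and all five differ in the same direction.

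**Step 3. What this means for a single result**

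- Hepatic Grade 4 and creatinine Grade 4: both texts say stop at once, so there is no conflict.
- Hepatic Grade 3 and creatinine Grade 3: 14.2.8 allows confirmation first; Table 2 stops at once.
- Hepatic Grade 2: 14.2.8 allows dosing to continue; Table 2 stops after confirmation.
- Creatinine Grade 2: 14.2.8 allows dosing to continue; Table 2 stops at once.
- Creatinine Grade 1: 14.2.8 is silent; Table 2 stops after confirmation.

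**Step 4. Cross-check within Section 14**

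For a confirmed Grade 2 bilirubin, 14.2.5 calls for interruption and cites Table 2. Read as covering bilirubin, 14.2.8 allows dosing to continue. Two subsections of the same rationale chapter therefore differ.

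**Step 5. The continue column**

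Entries: 0 of 7 rows in the protocol and 0 of 7 in the SAP. The two copies came through text extraction in different table layouts and both are blank, so an extraction fault is unlikely. The original PDF would settle it. The tier announced in 6.3.1 and 14.2.3 has no content in either document.

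**The case against.** The strongest reply is that 14.2.8 was never meant to restate Table 2. Its heading is Other Abnormalities, and it follows separate renal (14.2.4) and hepatic (14.2.5) sections that agree with Table 2 on cystatin C, BUN and Grade 2 bilirubin. It speaks of general intent, uses permissive verbs for Grades 2 and 3, and asks for flexibility. Section 6.3.1 also has a general sentence on which grades count as clinically significant, and 14.2.8 might echo that sentence instead of the table.

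Part of this stands. The paragraph is rationale, it points to the section that holds the operative table, and its scope is ambiguous. The reply does not remove the conflict:

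- 14.2.8 excludes no Table 2 parameter.
- Its three tiers follow Table 2's three columns.
- The general sentence in 6.3.1 concerns clinical significance, not whether to stop, confirm or continue. No other grade-by-action scheme exists in 6.3.1.
- Section 14.2.3 uses the word other in a way that includes hepatic abnormalities.

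A second reply is that the blank column is editorial, since every listed parameter already has two defined actions. That is fair: the blank changes no instruction for a listed value. The text still promises thresholds that are not there.

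A reader might infer more than the documents support:

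- *That investigators would keep dosing where Table 2 says stop.* This is not shown. Sections 14.2.3, 14.2.5 and 14.2.8 all send the reader to 6.3.1 or Table 2, and 14.2.9 calls interruption the primary response.
- *That interruption data would differ between sites.* No figure supports this, and SAP 4.9 summarises interruptions overall, with no comparison of sites.
- *That the SAP analysis is wrong.* SAP Table 2 matches the protocol table, and SAP 4.10.2 tabulates by those categories, not by 14.2.8.

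**Conclusion.** The point holds as an internal inconsistency that is wrong as written. Section 14.2.8 states the interruption triggers more leniently than Table 2 for all five graded parameters, by one grade for bilirubin, ALT, AST and GGT and by two for creatinine. It also differs from 14.2.5 on Grade 2 bilirubin. Separately, the continue thresholds announced in 6.3.1 and 14.2.3 are missing from all seven rows of Table 2.

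The consequence is a risk that the same laboratory value is handled under two readings. Nothing in the documents shows that this happened. The conclusion rests on two assumptions: that 14.2.8 covers Table 2 parameters, which its wording allows but does not state, and that the third column is blank in the original files.

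The practical weight is limited. Table 2 is the operative text, and SAP 2.1 records early termination of the study in March 2017. For this study, a correction would mainly help whoever interprets and reports the interruptions.

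**What to change.** The sponsor should make two wording changes in the protocol:

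1. Reconcile 14.2.8 with Table 2, or state explicitly that 14.2.8 applies only to abnormalities not listed there. If the second route is taken, the reference "Recommendations for interruption of dosing are provided in Section 6.3.1" also needs attention, because for unlisted abnormalities 6.3.1 gives investigator judgement and no graded scheme.
2. Reconcile the statements in 6.3.1 and 14.2.3 about continuing drug with the empty column, by settling whether that column was meant to have content.

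Which thresholds are right is for the sponsor and its clinical experts; nothing here favours one version. SAP Table 2 needs a change only if protocol Table 2 changes. The cost is protocol wording, with no new data and no new analysis.
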